5.1. In silico developments

In our laboratory, we have developed a comprehensive methodology for transcriptome analysis that combines extensive bioinformatic processing of biological samples with deep learning algorithms for interpretation. This approach enables the incorporation of all genes read in a sequence, performing classifications using a supervised method. Our algorithm has demonstrated robustness and high accuracy in preliminary tests.

The development consists of a pipeline that analyzes the RNA-seq sample in its crudest state, including coding and non-coding RNAs, circular RNAs, and the blood microbiome. The algorithm is trained on a cohort of previously classified samples and later validated using 10% to 20% of the samples.

To assess the algorithm's efficiency, we analyzed different RNA-seq databases available in digital repositories. Initially, we used the [GTEx database](#), containing 11,866 sequences from 30 different tissues obtained postmortem from dozens of individuals. Our algorithm achieved 99.1% accuracy in correct prediction (Figure 1), with only a few errors corresponding to potentially similar tissues (e.g., breast and fatty tissue).

Figure 1: Confusion matrix for normal tissue samples. The graph shows the intersection of the algorithm's prediction and the actual sample. Thus, the descending central diagonal from left to right shows the coincidence between the real and the predicted. Outside this diagonal, the numbers represent the algorithm's classification errors. As can be seen, they are infrequent.

We also analyzed the [Genomic Data Commons \(GDC\) database](#), containing RNA sequencing of biopsies from 34 different tumors with 10,000 samples. The algorithm's predictive capacity was again high, reaching 97.5% accuracy (Figure 2). These results demonstrate the algorithm's excellent classification capability for multiple samples.

Figure 2: Confusion matrix for tumor tissue samples. The graph has the same meaning as in the previous figure. Again, the number of mistakes outside the diagonal line is very low.

A sensitivity analysis of the algorithm was performed using 100 random samples from brain tumors in the GDC database. The algorithm achieved 100% precision (ROC of 1) and exhibited efficient behavior with a low number of clinical cases, reflecting the fundamental differences in gene expression between the two groups of tumors.

The aforementioned results were obtained from solid tissue RNA-Seq samples (biopsies). It is worth noting that blood cells may exhibit transcriptomic alterations in the presence of solid tumors or systemic diseases. Therefore, we analyzed different datasets

in various contexts, including samples obtained by Best et al⁴⁰ from patients with different solid tumors. The algorithm showed an AUC of 1 for detecting the presence of tumors in all cases.

We also analyzed samples from Cassetta et al on monocytes from patients with breast or endometrial cancer compared to healthy subjects⁴¹, and the algorithm achieved 100% prediction capacity. Moreover, we analyzed the dataset generated by Scharer et al on patients with lupus compared to healthy subjects, and the classification was excellent (AUC of 1)⁴².

In conclusion, our pipeline and the analyses performed demonstrate the ability to classify transcriptomics samples accurately. The algorithm is robust and extremely sensitive, primarily due to the large number of gene variants considered (approximately 200,000) and the unprecedented capacity of neural networks to interpret this vast amount of information. These findings lead us to propose that our pipeline may be useful in detecting tumor pathologies in peripheral blood transcriptomics.

5.2. Preliminary studies

We have previously developed a clinical protocol aimed at refining the methodology that will be employed in this study. The initial objective was to establish a reliable process for blood collection, RNA isolation, library generation for sequencing, and RNA sequencing. The preliminary results of these steps, conducted on 540 samples from three different studies, are described below.

First, we established a robust methodology for obtaining RNA samples from peripheral whole blood without cell separation. Samples were collected in PaxGene RNA tubes through antecubital vein puncture, and no adverse effects were observed in this procedure. The samples were stored at -20°C until RNA extraction, which was carried out

⁴⁰ "RNA-Seq of Tumor-Educated Platelets Enables Blood-Based Pan"
<https://pubmed.ncbi.nlm.nih.gov/26525104/>. Accessed 10 Apr. 2023.

⁴¹ "Human Tumor-Associated Macrophage and Monocyte" 15 Apr. 2019,
<https://scholars.duke.edu/individual/pub1379736>. Accessed 10 Apr. 2023.

⁴² "Epigenetic programming underpins B cell dysfunction in human SLE."
<https://pubmed.ncbi.nlm.nih.gov/31263277/>. Accessed 10 Apr. 2023.

using a specific kit from Thermo-Fischer. This approach allowed us to consistently obtain RNA samples in sufficient quantities for sequencing in all cases.

Next, we constructed the library, a process in which the RNA is converted into cDNA (complementary DNA). The RNA corresponding to ribosomes and globin is then extracted, fragmented, and adapters are added to the ends. The library construction proved robust for all analyzed samples.

Subsequently, we performed RNA sequencing at a depth of 100 million reads. Between 20,000 and 25,000 genes expressed in peripheral blood were detected across all samples (n=540). In a subset of patients, computed tomography was carried out to determine the degree of calcification in the coronary arteries (Coronary Calcium Score, CCS). We analyzed gene expression in peripheral blood and identified genes related to the degree of coronary calcification (Figure 3).

[figure not shown]

Figure 3: Preliminary results. We analyzed 38 samples from patients who had coronary calcium measured. The left panel shows the result of a PCA analysis where a moderate but significant reduction in dimensionality is found based on the extent of coronary calcification. The heatmap shows the differentially expressed genes between the two groups.

6. Study Objectives

6.1 Primary Objective

The main objective of this study is to investigate the diagnostic accuracy of whole-blood transcriptome analyzed by artificial intelligence in detecting the presence and extent of coronary atherosclerosis in stable patients with suspected or known coronary artery disease (CAD), using coronary computed tomography angiography (CCTA) images.

Specific aims:

I) To classify patient transcriptomes based on the presence and extent of the following CCTA outcomes:

- Coronary calcium score
- Total coronary plaque burden
- Degree of coronary stenosis
- Coronary high-risk plaques (low-attenuation, positive remodeling; spotty calcification, or napkin-ring sign)

II) To train artificial intelligence algorithms using information from the transcriptome to recognize the outcomes of interest in the training set.

III) To explore the diagnostic accuracy (sensitivity and specificity) of the method in detecting the presence, absence, or extent of the outcomes of interest in the validation/test set.

6.2 Secondary Objectives:

The secondary objectives of this study are as follows:

6.2.1 To explore the diagnostic accuracy of whole-blood transcriptome in relation to other outcomes of interest provided by CCTA images, including:

- Presence and extent of aortic calcification
- Hepatic steatosis
- Flow limiting artery obstruction (coronary fractional flow reserve)
- Coronary artery inflammation (perivascular fat attenuation index)
- Total epicardial adipose tissue volume

6.2.2 To calculate the polygenic risk score (PRS) from the transcriptome and explore its association with the previously described outcomes of interest.

6.2.3 To explore the differences in transcriptomics of peripheral blood between patients who did and did not develop a cardiovascular event during follow-up.

7. Methods

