9.4. Bioinformatic and computational analysis of the transcriptomics sample

The bioinformatic analysis of the sequenced samples will be performed from the .fastq files containing the raw data. These files will be fed to a *pipeline* analysis which comprises a successive series of bioinformatic procedures, including sample quality control, alignment with the human genome and count of *reads* per identified gene. The transcripts to be identified correspond to:

- Linear RNA identification, including mRNA and non-coding RNAs.
- circRNA (circular RNA)
- Alternative splicing variant identification
- Blood microbiome
- Variant calling for Polygenic risk score calculation (from RNA).

The expression quantification of the transcripts is then transformed using a series of proprietary routines, to then be transformed into an image (US patent 62/944,063 (pending)). This image represents both the expression of the transcripts as a function of their expression level and the genomic position as well as the RNA subtype. The set of images, which represent the set of gene expression in peripheral blood, is subsequently entered into a neural network to generate training that classifies the samples accordingly.

Once the bioinformatic analyses are done, we will use that information to train machine and deep learning models to predict those patients with coronary artery disease. The following ML/DL approaches will be used:

- Classical machine learning algorithms, including xgboost.
- Convolved Neural Networks (CNN) through our patented technology of gene expression conversion.
- Graph neural networks.
- Natural processing language by using reads.

All these bioinformatic and artificial intelligence procedures will be carried out using free-use programs (“open access software”) under a routine created by the study

researchers, mainly using python for coding and pyTorch for the training of the neural network.

Data will be stored and analyzed at the cloud provider at the moment of analysis (currently AWS or Google Cloud) under strict cybersecurity measures.

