9.5. Analysis of Coronary Computed Tomography Angiography

Coronary Calcium scoring will be analyzed using dedicated software (HeartBeat-CS, Philips Healthcare, Best, The Netherlands) by an experienced observer blinded to the clinical characteristics, laboratory, and transcriptome results. The presence of CAC and its extension will be evaluated using both ordinal variables (number of segments with CAC and number of affected vessels, and qualitatively: absence, mild, moderate, and severe) and continuous variables (Agatston units). The presence and extension of calcifications at the level of the aortic valve and the thoracic aorta (Agatston units) will also be evaluated independently. The extent of aortic calcification will be evaluated in sections that include the area ranging from the bifurcation of the pulmonary artery as the upper limit to the diaphragm as the lower limit.

CCTA images will be anonymised locally and transferred to a core laboratory located in Oxford, UK, for analysis of secondary outcomes by investigators who will be unaware of population demographics and outcomes. The presence of obstructive CAD will be defined as the presence of at least one lesion causing a luminal stenosis of 50% or larger. The extent of coronary artery disease using the modified Duke coronary artery disease index, as follows (Group 1: <50% stenosis; Group 2: ≥ 2 mild stenosis with proximal CAD in 1 artery or 1 moderate stenosis; Group 3: 2 moderate stenosis or 1 severe stenosis; Group 4: 3 moderate stenosis, 2 severe stenosis, or severe stenosis in the proximal left anterior descending (LAD) artery; Group 5: 3 severe stenosis or 2 severe stenosis in the proximal LAD; Group 6: $\geq 50\%$ stenosis in left main coronary artery). The presence of high-risk plaque features (spotty calcification, low-attenuation plaque, positive remodeling, and napkin-ring sign) will be explored. The total epicardial adipose tissue volume will be calculated in a semi-automated manner by tracking the contour of the pericardium from

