10.2. Data quality assurance and control

a. Data quality assurance and storage

This study will implement a standardized data collection process, since trained interviewers will ensure data collection uniformly across all respondents, properly fill out the forms and handle sensitive information.

Baseline data entry and storage will be performed using the electronic platform RedCap. This electronic data capture platform is covered by security systems, in compliance with current regulations on data protection. The access control will be

configured in such a way that there are two users with the project administrator role, who will be in charge of authorizing the access of the study personnel, as necessary, and with access levels according to the roles and responsibilities. The electronic forms that will be used for data upload will be specifically designed for this study. The data will be entered by the researcher at the recruitment center, via the web. The personnel in charge of entering the data will be trained in the use of RedCap for this purpose.

The study data corresponding to the Follow-up stage will be collected on paper-based forms. The forms will contain validated questions usually used in previous clinical studies.

At the sites, the anonymised paper-based forms will be scanned by trained personnel and stored in a secure location to protect sensitive information from unauthorized access. All anonymized digital forms, CCTA images, genetic data and laboratory reports will be encrypted and stored on a central outsourced AWS server. The access will be configured in such a way that there are two owners with the project administrator role, who will be in charge of authorizing the access of the study personnel, as necessary, and with access levels according to the roles and responsibilities.

A random quality check will be implemented on a sample of completed forms for accuracy and completeness to ensure that the data collected is reliable.

The study data will then be stored on a central outsourced server (AWS).

b. Data Entry

Trained and certified personnel will enter the digital data in an Excel format document located in the AWS server.

The following quality controls will be carried out:

- Validation rules generated according to the nature of the variables, programmed through the data validation modules available in Excel.
- Query generation according to pre-established validation rules, to be answered by researchers on the sites.

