10.4. Calculation of the sample size

The calculation of the number of patients to demonstrate a positive effect for the use of peripheral blood transcriptomics for the diagnosis of the presence of severe coronary calcification is carried out based on previous experiences by the group of researchers. There is still no standardized methodology in the medical literature to perform the sample calculation of this type of analysis, since it is very recent and is in the exploration phase. *In silico* studies carried out by this group of researchers and the preliminary clinical studies carried out previously showed that at least a sample of 150 patients is necessary for the initial training of the artificial intelligence algorithm that detects transcriptional differences between patients with or without a solid tumor. (for example, breast tumor). Therefore, 200 patients will be included based on the minimum number necessary to perform the initial training of an artificial intelligence algorithm.

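### One validation/test set serves four model families with no lead model named, so reported accuracy may be optimistic if that set is also used to choose the model

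*Protocol*

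**What the plan says.** - **Sets.** Protocol 6.1 names two sets. Aim II trains in a training set. Aim III explores sensitivity and specificity "in detecting the presence, absence, or extent of the outcomes of interest in the validation/test set". Section 5.1 describes the group's existing pipeline with the same two-part pattern: "The algorithm is trained on a cohort of previously classified samples and later validated using 10% to 20% of the samples".
- **Models.** Section 9.4 states "The following ML/DL approaches will be used" and lists classical machine learning including xgboost, convolutional networks, graph networks and language processing on reads. It names no lead model and no rule for choosing among them.
- **Reporting.** Aim III refers to one method, and section 10.5 gives an AUC for one trained algorithm.
- **Size.** Section 10.4 says that "at least a sample of 150 patients is necessary for the initial training of the artificial intelligence algorithm" and concludes: "Therefore, 200 patients will be included based on the minimum number necessary to perform the initial training".
- **Masking and access.** In section 9.5 the calcium score is read "by an experienced observer blinded to the clinical characteristics, laboratory, and transcriptome results". Section 10.2 keeps images, forms and genetic data on one central server with access levels set by role. It does not say whether any role is kept from the test patients' CT results.

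**The concern.** Two jobs need labelled patients outside model fitting: choosing among models (with their tuning settings and thresholds), and measuring the accuracy of the model chosen. Section 6.1 gives both names, validation and test, to one set. With four families planned and one result to report, a choice has to be made somewhere, and the plan names no other labelled set outside training in which to make it.

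If the choice is made on the set from which accuracy is reported, the reported figure is the maximum of several noisy estimates. It is biased upward even when every model is useless. The hold-out can only be a few dozen patients, so that noise is large. The protocol also supplies a benchmark that this bias can reach: section 4.1 puts the AUC of existing risk methods at 0.60 to 0.65.

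**Working it through.** **Hold-out size.** The plan fixes none, and the 200 cannot be re-derived because section 10.4 gives no target accuracy, prevalence or precision. Two readings are possible:
- Share in section 5.1: 10% to 20% of 200 = 20 to 40 patients.
- Training minimum in section 10.4: 200 − 150 = 50 patients.

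**Assumptions not in the protocol.** Prevalence is 30%, giving 6, 12 or 15 cases at n = 20, 40 or 50. There is one final version of each of four equally good models. Scores are normal in cases and non-cases, with between-model correlation of 0 to 0.8.

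**Closed form for worthless models (true AUC 0.50).** With n1 cases and n0 non-cases, the standard error of one AUC is √[(n1 + n0 + 1)/(12·n1·n0)]:
- n = 20: √[21/(12·6·14)] = √(21/1008) = 0.144
- n = 40: √[41/(12·12·28)] = √(41/4032) = 0.101
- n = 50: √[51/(12·15·35)] = √(51/6300) = 0.090

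The expected maximum of four independent standard normals is 1.03. The best of four uncorrelated models therefore averages 0.50 + 1.03 × SE = 0.65, 0.60 and 0.59. If the AUCs have correlation r, the excess shrinks by √(1 − r). A score correlation of 0.8 gives r ≈ (6/π)·arcsin(0.4) = 0.79, so the factor is about 0.46 and the averages become 0.57, 0.55 and 0.54.

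**Simulation (20,000 replicates per setting, Mann-Whitney AUC), mean reported AUC:**

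| True AUC | n | One fixed model | Best of 4, corr. 0 | corr. 0.6 | corr. 0.8 |
|---|---|---|---|---|---|
| 0.50 | 20 | 0.50 | 0.65 | 0.60 | 0.57 |
| 0.50 | 40 | 0.50 | 0.60 | 0.57 | 0.55 |
| 0.50 | 50 | 0.50 | 0.59 | 0.56 | 0.54 |
| 0.65 | 20 | 0.65 | 0.79 | 0.74 | 0.72 |
| 0.65 | 40 | 0.65 | 0.75 | 0.71 | 0.70 |
| 0.65 | 50 | 0.65 | 0.74 | 0.71 | 0.69 |

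**Chance that a worthless method shows an AUC above 0.65** (correlation 0.8 to 0):
- n = 20: about 15% for one fixed model, 29% to 49% for the best of four
- n = 40: about 7%, against 15% to 25%
- n = 50: about 5%, against 10% to 18%

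**Sensitivity.** With prevalence of 20% or 50%, true AUC of 0.50, 0.65 or 0.80, correlation of 0 to 0.8 and n of 20 to 50, the optimism runs from +0.03 to +0.17. One model fixed beforehand shows none. Repeated tuning on the same set would add to these figures, which count only one choice among four finished models.

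**The case against.** No passage says that the four families compete on the hold-out or that only the best will be reported. In section 5.1, validation means evaluation after training, so the slash in section 6.1 may simply join two names for one untouched set. Split rules, model selection and model lock often sit in an SAP, which is not shown. The aim is worded as exploration, with no success threshold. Four models fed the same transcriptomes will be highly correlated, which shrinks the bias. A sealed test set of 20 to 40 patients would hold only 6 to 12 cases at 30% prevalence, and a sensitivity of 9/12 has an exact 95% interval of about 43% to 95%.

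Much of this stands. The bias is conditional, which is why the point says may and not will. High correlation reduces the bias but does not remove it: at 0.8 the excess for worthless models is still 0.04 to 0.07. The imprecision of a small sealed set is real and is the reason to allow nested cross-validation. The SAP argument does not dispose of the point, because the merged set is wording in the primary objective, and test labels have to be withheld before modelling starts. A later analysis document cannot undo their release.

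A reader might go further and infer three things that the protocol does not support:
- **That the modellers are unblinded to the test labels.** The protocol is silent. Supervised training needs the training labels in any case, so only the test labels are at issue.
- **That keeping images and genetic data on one server is leakage.** The statement "All anonymized digital forms, CCTA images, genetic data and laboratory reports will be encrypted and stored on a central outsourced AWS server" is followed in section 10.2 by access levels set by role, and section 9.4 leaves the choice of analysis cloud open.
- **That all CT readers are blinded to the transcriptome.** Section 9.5 says so only for the calcium reader. The core-laboratory readers are described as unaware of demographics and outcomes, and the transcriptome is not mentioned.

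**Conclusion.** The point holds in conditional form. The plan merges validation and test into one set, lists four model families with no lead, and reports one accuracy result. If the set is used for tuning or selection, a worthless method would be reported with a mean AUC of about 0.54 to 0.65 (0.54 to 0.59 at n = 50), and a true AUC of 0.65 as about 0.69 to 0.79. The upper end for a worthless method reaches the range that section 4.1 gives for existing methods.

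These sizes rest on assumed prevalence, correlation and equal model quality, and on a hold-out size inferred from sections 5.1 and 10.4. The selection bias is zero if one model is fixed in advance or if all four results are reported. This is a cheap improvement that should be made before modelling begins. It is not evidence that the study will mislead.

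**What to change.** In section 6.1 aim III and section 9.4:
1. Do all tuning, and the choice among the four families, by cross-validation inside the training set. No third set is needed, so the final model can still be fitted on the 150 patients that section 10.4 requires.
2. Name a separate test set and draw its IDs before modelling starts.
3. Withhold those patients' CCTA results from the modellers through the role-based access already described in section 10.2.
4. Lock one model and one threshold per outcome, score the test set once, and report the other models' test results as exploratory.

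Nested cross-validation over all 200 patients is an acceptable alternative, provided that every tuning and selection step is repeated inside each outer fold. At 30% prevalence it would base the accuracy estimate on 0.30 × 200 = 60 cases, against 6 to 15 in a hold-out of 20 to 50.

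The cost is protocol wording and an access setting, with no extra patients or procedures. The drawback is that the test set cannot be reused for tuning and the stated accuracy will probably be lower.
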